7.1 Diversity and Patient and public involvement

Participants will be surveyed at the end of each dietary arm to assess how easy each diet was to adhere to and whether they have any suggestions about the protocol.

We will aim to recruit a diverse range of participants (gender and ethnicity) to reflect the local population in Bristol.

7.2 End of study definition

When last participant has completed final visit and any follow-up monitoring, and data collection is finalised.

8. Outcomes and Statistics

Primary outcome:

- Difference in aldosterone profiles as measured by cosinor analysis of the 24-hour curves and dynamic markers.
- Dynamic markers include: total area under the curve, magnitude of morning peak, number of peaks, or evening nadir.

Secondary outcomes:

- Difference in magnitude of renin or aldosterone response to change in posture
- Difference in magnitude of aldosterone response to exercise
- Difference in 24-hour urine aldosterone

9. Ethical Considerations

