Salt intake is known to effect plasma renin activity and consequently aldosterone concentration. This was not controlled in the U-Rhythm pilot study. We hypothesise that variation in salt intake may, at least in part, explain the different patterns observed. If the hypothesis is correct, we would expect a high salt diet to lead to a diurnal (ACTH dependent) pattern of aldosterone as we expect salt would reduce the levels of renin and angiotensin 2. Conversely, we would expect a low salt diet to result in greater levels of renin and angiotensin 2 resulting in a non- ACTH dependent ultradian rhythm of aldosterone concentration.

[figure not shown]

Figure 1: Figure from Upton et al (2003)[1] showing how cortisol and aldosterone varied in 2 healthy volunteers. Note how aldosterone (blue line) follows cortisol (red line) closely in panel B, however there is very little correlation in panel C. We wish to explore whether salt intake may explain the difference in healthy volunteers.

Learning how salt intake affects dynamic changes in aldosterone secretion- especially overnight- may lead to improved methods for diagnosing abnormal patterns of aldosterone levels and thereby allow improved therapy.

5. Aims and hypothesis

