5.2 Hypothesis

The high salt diet and low salt diet will have difference aldosterone profiles. Specifically, we expect the high salt diet will lead to a diurnal rhythm (as renin may be suppressed, meaning the dominant regulatory factor is ACTH) and low salt diet an ultradian rhythm (with renin as the primary regulator).

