5.3 Null hypothesis

There will be no difference in aldosterone profiles between study arms.

6. Participants and recruitment

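### The primary measures in section 8 do not isolate the diurnal-versus-ultradian change of section 5.2, and no outcome measures how closely aldosterone follows cortisol

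*Protocol*

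**What the plan says.** The hypothesis (protocol section 5.2) concerns the type of rhythm and its regulator. For high salt, "we expect the high salt diet will lead to a diurnal rhythm (as renin may be suppressed, meaning the dominant regulatory factor is ACTH"); for low salt, "low salt diet an ultradian rhythm (with renin as the primary regulator"). The null in section 5.3 is much broader: "There will be no difference in aldosterone profiles between study arms".

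The background text before section 5 gives two reasons for the study. One is a contrast between two volunteers in Figure 1: "Note how aldosterone (blue line) follows cortisol (red line) closely in panel B, however there is very little correlation in panel C". The other is an effect on level that is treated as established: "Salt intake is known to effect plasma renin activity and consequently aldosterone concentration". It adds that "we would expect a low salt diet to result in greater levels of renin and angiotensin 2".

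Section 8 sets the primary outcome as "Difference in aldosterone profiles as measured by cosinor analysis of the 24-hour curves and dynamic markers" and continues: "Dynamic markers include: total area under the curve, magnitude of morning peak, number of peaks, or evening nadir". The secondary outcomes are the responses to posture and to exercise, and urinary aldosterone over 24 hours. None of them relates aldosterone to cortisol or ACTH. The opening summary says that further hormones will be monitored with the U-Rhythm device, but it does not name them, and section 8 does not use them.

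**The concern.** The specific prediction is about shape and regulation, whereas most of the listed measures are about size. If low salt simply raises aldosterone throughout the day, AUC, morning peak, nadir, mesor and amplitude all change together and the section 5.3 null falls. That result would be correct as far as the null goes. It could then be read as support for section 5.2, although no rhythm had changed.

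The feature that separates the two volunteers in Figure 1, whether aldosterone tracks cortisol, would also go unmeasured. The pilot is meant as a step towards better diagnosis, so the next study could be designed on a rhythm effect that was really a level effect.

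**Working it through.** **Inputs.** From the documents: 12 participants in a crossover, hence 12 pairs, and the measures listed in section 8. The protocol gives no power inputs, cosinor period, peak-detection rule or sampling interval, so there is no figure to reproduce. Everything else is assumed: 20-minute samples (72 per 24 h) and the curve shapes below.

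**1. Scaling.** Multiply a profile by k. AUC, mesor, amplitude, peak and nadir are all multiplied by k; amplitude/mesor and R² are unchanged. For a diurnal curve with mean 100 and amplitude 50, taking k = 3:

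| | mesor | amplitude | AUC | morning peak | nadir | amplitude/mesor |
|---|---|---|---|---|---|---|
| k = 1 | 100 | 50 | 2400 | 150 | 50 | 0.5 |
| k = 3 | 300 | 150 | 7200 | 450 | 150 | 0.5 |

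A peak count is level-free only if its threshold is relative. A 3-h pulse train of amplitude 15 on mean 100 shows 0 peaks at a fixed prominence of 40 units. Tripled, it shows 7. With a threshold of 40% of mesor the count is 0 both times.

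**2. Single-period 24-h cosinor, if that is what is used.** A pulse component whose period divides 24 h evenly is orthogonal to the 24-h terms, so mesor, amplitude and acrophase do not change. Only the fit changes: R² = A²/(A² + B²), with 24-h amplitude A and pulse amplitude B. With A = 0.30:

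- B = 0.2: 0.09/0.13 = 0.69
- B = 0.4: 0.09/0.25 = 0.36
- B = 0.6: 0.09/0.45 = 0.20

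For pulse periods of 5, 7 and 10 h and amplitude 50, only 4.1 to 7.4 units leak into the 24-h amplitude (R² at most 0.023). Adding a 3-h term to the model recovers a 3-h pulse amplitude of 50 in full.

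**3. Coupling.** Let cortisol have 24-h and 1.5-h amplitudes of 60 and 20. Let two aldosterone curves each have amplitudes 30 and 30, with the pulses in phase with cortisol in one and in antiphase in the other. The variances are (60² + 20²)/2 = 2000 and (30² + 30²)/2 = 900, and √(2000 × 900) = 1341.6.

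- In phase: covariance (60×30 + 20×30)/2 = 1200, r = 1200/1341.6 = 0.89
- Antiphase: covariance (60×30 − 20×30)/2 = 600, r = 600/1341.6 = 0.45

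Mesor, amplitude and AUC are identical in the two. Peak count (16 v 15), morning peak (160 v 158) and nadir (42 v 40) hardly differ.

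**4. Rejection rates.** Simulation of 12 pairs, 300 replicates, paired t-test at two-sided 0.05. Assumed: mean 100, 24-h amplitude 50% of mean, 2.5-h pulses of 40%, between-person log-SD 0.4, visit-to-visit log-SD 0.25, 10% sample noise.

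| Scenario | mesor | amplitude | amplitude/mesor | AUC | morning peak | nadir | peaks, fixed threshold | peaks, relative threshold |
|---|---|---|---|---|---|---|---|---|
| No change | 0.04 | 0.04 | 0.06 | 0.04 | 0.06 | 0.05 | 0.04 | 0.07 |
| Level doubled, same shape | 0.99 | 0.99 | 0.08 | 0.99 | 0.99 | 0.99 | 0.97 | 0.05 |
| Pulses added to diurnal rhythm | 0.04 | 0.03 | 0.10 | 0.04 | 0.26 | 1.00 | 1.00 | 1.00 |
| Diurnal replaced by pulses | 0.02 | 1.00 | 1.00 | 0.02 | 0.16 | 0.49 | 1.00 | 1.00 |

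The nadir also reacts to added pulses, because pulse troughs lower the minimum. It reacts just as strongly to level, so it cannot say which has changed.

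**The case against.** A reader might infer that the primary measures do not test section 5.2 at all. The documents do not support that.

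- Number of peaks is a listed primary marker and responds to an ultradian rhythm: 1 peak for the diurnal curve, 8 for a 3-h one, with rejection in 1.00 of replicates in both pulse scenarios.
- A complete switch from diurnal to ultradian lowers even the single-period 24-h amplitude (1.00). That amplitude misses only pulses laid over a preserved diurnal rhythm.
- In section 8, 24-hour describes the curves. It does not fix a single 24-h period, so a multi-component fit is open, and the choice may stand in an analysis plan that is not shown.
- A reader might also infer that peak counting is biased by level. The protocol states no fixed threshold or assay floor, so that remains a possibility and is not a defect of the text.
- Level belongs to the question. The opening summary states the aim in terms of aldosterone levels, and the section 5.3 null covers any difference in profile. Rejecting it on level is legitimate.

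All of this stands, and it limits the point. It does not remove it. Cosinor components and peak rules can wait for an analysis plan, but section 8 itself fixes which quantities are outcomes. It does not say which of them bears on section 5.2, and it omits the association with cortisol. That association would not be a direct test of ACTH dependence either: no ACTH measurement is described, and two hormones that each follow the clock will correlate.

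**Conclusion.** The point holds in a limited form, at moderate severity. The primary set does not isolate the diurnal-versus-ultradian change. AUC, morning peak, nadir and unnormalised mesor and amplitude confound rhythm with a level that the protocol already expects salt to move. Only number of peaks addresses the ultradian half directly, and the Figure 1 contrast is in no outcome.

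The scaling result, and the unchanged 24-h terms for pulse periods that divide 24 h evenly, are exact. The rejection rates and the correlations of 0.89 and 0.45 are illustrative and depend on assumed curves, noise and sampling interval. That cortisol could be taken from the same U-Rhythm samples is an inference from the steroid sampling and Figure 1; the protocol does not state that it will be assayed.

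**What to change.** In section 8:

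1. Name one level-independent rhythm measure as the test of section 5.2, computed on log-transformed or mean-normalised profiles and compared within person. Candidates are amplitude/mesor, variance explained by the 24-h component, or a multi-component cosinor. The choice matters. Amplitude/mesor detects loss of the diurnal rhythm but hardly registers added pulses (0.10 in the table), whereas variance explained and the multi-component fit respond to both. Detect peaks relative to level.
2. Add the within-person aldosterone–cortisol association, compared between diets, as a secondary outcome. Describe it as indirect evidence of ACTH dependence, and confirm that cortisol is among the further hormones assayed.
3. Keep AUC as the measure of level, and state that a difference in level alone does not support the rhythm hypothesis.

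The cost is a short rewording of section 8, some extra analysis code and one more outcome in a 12-person pilot. If cortisol is not yet among the planned assays, there is that assay as well.

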9.1 Safety

9.1.1 Screening procedures

The risk associated with conducting screening procedures is identification of incidental findings. Should abnormalities in ECG and blood pressure monitoring and / or pregnancy test identified, the participant will be informed, as they may be unable to participate in the rest of the study. With the participant's permission, their GP will be informed of the findings in writing and the participant will be encouraged to see their GP about the results.

9.1.2 Venepuncture

Risks to the participant of venepuncture include phlebitis, failure to access the vein, thrombophlebitis, bruising and localised pain at the insertion site, clot formation and introduction of flora to site precipitating infection. To minimise these risks, venepuncture will be performed by a doctor or suitably qualified member of the research team. The risk of venepuncture to the qualified professional performing venepuncture is needle-stick injury. This risk will be minimised by following trust guidelines on venepuncture, using the appropriate sharps disposal units in accordance with guidance and by following Trust guidance in the incidence of needle-stick injury. The total blood volume drawn will not exceed 50mL and will not have any haemodynamic consequences to the participant.

9.1.3 Microdialysis catheter insertion

This study will present minimal risk to participants. The microdialysis procedure has previously been conducted in hundreds of participants with no significant adverse events (e.g. ULTRADIAN, REC 16/SW/0069, NCT02934399; REC 47081; REC 77081, [1,5–7]. There is a possibility of minor bruising at the site of the microdialysis probe insertion. The procedure is minimally invasive. A fine catheter is inserted just beneath the surface of the skin using aseptic technique. The catheter remains in place for approximately 24 hours and the risk of infection are considered minimal. The probe, microdialysis pump and accessories used for the subcutaneous tissue collection device are commercially available (CE marked) and no problems are anticipated in relation to these items.

Study protocol v3 31/07/2025

IRAS: 354064

The CGMS sensor is a CE marked device. This is inserted into clean skin of the abdomen or arm by the study investigator (contralateral side to microdialysis probe) following manufacturer recommended standard procedure. This is considered a very low risk procedure.

All other sensors are non-invasive and simply require contact with the skin. There is no anticipated risk associated with these devices.

9.1.4 Ramped exercise tolerance testing

Exercise-induced changes in blood pressure may be experienced by some participants. Either an increase or decrease, during and / or after exercise may occur. A research nurse or doctor will be always present, with continuous ECG and blood pressure monitoring. Any adverse changes will be acted upon. The protocol will be stopped immediately should any participant experience discomfort or distress.

9.1.5 Pregnancy testing

Premenopausal females will be asked to confirm that they are not pregnant and will be offered a pregnancy test prior to participating in the study to confirm they are not pregnant. This test is mandatory. The urine pregnancy test will be completed on all visit days (before commencing any procedures) by a researcher or research nurse.

9.2 Research Materials

9.2.2 Data

The data collected in this study will be for research purposes only. Data will be stored in linked-anonymised format and collected and kept in accordance with ICH-GCP guidelines in a secure, locked location. Participants will be able to view their results and receive an explanation from the investigator upon request.

9.2.2 Research Equipment

Participants will be asked to take utmost care of equipment loaned during the study however the study team will ultimately be responsible for any damage to equipment. No equipment will be loaned to the NHS site.

Study protocol v3 31/07/2025

IRAS: 354064

9.3 Specimen Handling and Laboratory Procedures

Venous blood will be collected by a research nurse or doctor. Samples will be labelled with Study name and ID number and participant age and sex. Labelling with age and sex facilitates quicker identification of results outside the normal range for the age/sex of the participant. Venous blood to be tested for renal function will be immediately placed in the appropriate sample tube, labelled, and stored on ice within a box. This will be stored within the study room until the study visit is completed at which point, the sample will be delivered by a researcher or research nurse to the UH Bristol and Weston Clinical Biochemistry department where they will be processed immediately. Additional serum samples will be processed at the Biomedical Sciences Building (University of Bristol) and stored there at -70°c for future analysis of hypertension biomarkers. Acellular interstitial fluid and urine samples will be securely sent to the University of Bergen for analysis.

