Day 1-6	Participant follows meal plan and keeps sleep diary Contact researcher if any issues (study email address: [contact] or designated phone number)	
Day 7	Participant starts 24-hour urine collection with 2 nd micturition of the day Study visit 2 (1 hour) [labelled visit 5 on 2 nd arm of study] - U-Rhythm set-up - Given sleep-recording device (Acu-Pebble or similar) - Given 24-hour diary Participant completes 24-hour diary (recording meal times,	NIHR CRF, [name]
Day 8	sleep/wake times and any exercise undertaken). 24-hour urine finishes after 1 st micturition of the day Study visit 3 (4 hours) [labelled visit 6 on 2 nd arm of study] - Weight and blood pressure measured - Participant adopts supine posture on arrival - Post-diet questionnaire - Blood tests (U&E, renin, and aldosterone after 30 mins lying then at 20, 40, and 60 minutes standing plus stored samples for future analysis) - Exercise on static bike (30 minutes at 50-60% VO2 peak) - Serum renin and aldo after exercise - U-rhythm disconnected 2 hours after exercise finish	NIHR CRF, [name]

- 24-hour urine sample, U-rhythm, and sleep device returned
- Diet protocol stopped after visit (i.e. after breakfast on day 8)
 unless there has been any issue with U-rhythm recording, in
 which was the participant will be asked to extend the study for a
 further day and conduct a full visit 3 or 6 the next day

If this is the participant's first arm of the study, arrange dates for 2^{nd} arm.

£150 compensation for time given in voucher form after completion of each arm of the study.

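### Section 9.3 keeps renal-function blood on ice until the visit ends, about 3.5 h for the supine draw at visits 3 and 6, which risks falsely raised potassium

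*Protocol*

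**What the plan says.** Section 9.3 of the protocol gives a handling rule for blood to be tested for renal function. It is to be "immediately placed in the appropriate sample tube, labelled, and stored on ice within a box". The next sentence sets how long it stays there: "This will be stored within the study room until the study visit is completed". Only then is it taken to Clinical Biochemistry, so the promise of immediate processing starts after the wait. For these tubes the section mentions neither separation before storage nor a time limit.

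The length of the wait follows from the Day 8 row of the schedule in section 7: "Study visit 3 (4 hours) [labelled visit 6 on 2 nd arm of study". The relevant entries are:

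- "Participant adopts supine posture on arrival"
- "Blood tests (U&E, renin, and aldosterone after 30 mins lying then at 20, 40, and 60 minutes standing"
- "Exercise on static bike (30 minutes at 50-60% VO2 peak"
- "Serum renin and aldo after exercise"
- "U-rhythm disconnected 2 hours after exercise finish"

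U&E is also taken on Day 0 (visit 1, or visit 4 in the second arm), which is scheduled for 1 hour.

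**The concern.** Chilling whole blood slows the red-cell sodium-potassium pump, and potassium leaks out of the cells. The measured concentration can then rise with time on ice even though the participant's potassium has not changed. This is general laboratory knowledge; the protocol does not discuss it and gives no rate. Because section 9.3 states no separation step, a tube handled as written is exposed to this for the whole hold.

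Three uses of the result are at stake:

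- **Absolute U&E values at visits 3 and 6.** Potassium stimulates aldosterone, the hormone under study, so these values are natural context for reading the profiles.
- **Any comparison of visits 3/6 with visits 1/4.** The holding times differ by hours.
- **Out-of-range flags.** Section 9.3 labels tubes with age and sex so that abnormal results are spotted faster, and section 10 sets out how incidental findings are reported. A storage artefact could cause a false alarm or hide a truly low value.

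**Working it through.** **Inputs.** All times are from the Day 8 row of the section 7 schedule: supine from arrival (t = 0); first draw after 30 min; standing draws 20, 40 and 60 min later; exercise for 30 min; U-Rhythm disconnected 120 min after exercise. The stated visit length is 4 h.

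**Step 1: reproduce the visit length.** 30 + 60 + 30 + 120 = 240 min = 4 h. This matches the stated length with no slack, so the holds below are the planned ones, not rare extremes. Transport time adds to them.

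**Step 2: holding time = 240 min minus draw time.**

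| Draw | Drawn at (min) | Hold on ice (min) | Hold (h) |
|---|---|---|---|
| Supine | 30 | 210 | 3.50 |
| Standing 20 min | 50 | 190 | 3.17 |
| Standing 40 min | 70 | 170 | 2.83 |
| Standing 60 min | 90 | 150 | 2.50 |

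The post-exercise sample is listed for renin and aldosterone only, so on either reading of the schedule no U&E draw comes after minute 90. The last 150 min of the hold serve no stated purpose for U&E. At visits 1 and 4 the hold cannot exceed about 60 min.

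**Step 3: possible size.** The drift rate is an assumption, because the documents give none. Taking a linear drift r between 0 and 0.2 mmol/L per hour, error = r × hold:

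| r (mmol/L per h) | Supine (3.5 h) | Standing 60 min (2.5 h) | Difference (1 h) |
|---|---|---|---|
| 0 | 0 | 0 | 0 |
| 0.05 | 0.17 | 0.12 | 0.05 |
| 0.1 | 0.35 | 0.25 | 0.10 |
| 0.2 | 0.70 | 0.50 | 0.20 |

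Against visits 1 and 4, the supine tube waits at least 3.5 − 1 = 2.5 h longer. At the top of the range that is a spurious rise of at least 2.5 × 0.2 = 0.5 mmol/L; at the bottom it is none.

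**Step 4: which draws include U&E.** The blood-test entry can be read as U&E, renin and aldosterone at all four draws, or as U&E once with the two hormones repeated. The last two columns of the Step 3 table apply only on the first reading. The supine column applies on either reading, if the single U&E is the supine one.

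**The case against.** The strongest reply is that little in the trial depends on this. Potassium is not a primary or secondary outcome in section 8, where the postural outcome concerns renin or aldosterone. Both arms use the same visit, draw times and holding rule, so a constant storage offset largely drops out of the within-person diet contrast. All of this stands. A reader might infer that the high- versus low-salt comparison is biased, or that potassium was planned as a check on the diets. The protocol supports neither: it gives U&E no such role, and the crossover handles both arms alike.

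A reader might also infer a definite false elevation, or a spurious fall from supine to standing. Neither is established. Direction and rate come from outside the documents, the lack of separation is inferred from silence, and the postural artefact needs U&E at every draw.

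Section 10 should not be overstated either. Its examples are ECG, blood pressure and pregnancy test, though given only as examples. The GP is told only with permission, and the letter to the participant is described for when that permission is refused. The long hold does not touch eligibility, since screening blood is drawn at the 1-hour visit.

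Finally, tube type, separation and time limits often sit in a laboratory manual. That would answer a complaint about missing detail. Here, however, the protocol gives a positive instruction to chill and to wait, and a manual that did otherwise would contradict it.

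**Conclusion.** The point holds as a handling risk. Followed as written, section 9.3 keeps renal-function blood on ice for about 3.5 h for the supine draw at visits 3 and 6, and for down to about 2.5 h for the last standing draw if U&E is repeated, against at most about 1 h at visits 1 and 4. These times follow from the protocol's own schedule.

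The effect on potassium is a risk of unknown size: 0 to 0.7 mmol/L for the supine tube, if blood is unseparated and drift is linear at 0 to 0.2 mmol/L per hour. It bears on absolute values, on comparison across visits and on out-of-range flags. It does not undermine the listed outcomes. The change is worth making because the rule is explicit, the wait has no stated purpose and the remedy is cheap.

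**What to change.** Amend section 9.3 so that U&E blood is not kept on ice and is separated, or delivered to Clinical Biochemistry, within a stated maximum time of each draw. At the latest this should be directly after the last U&E draw, not at the end of the visit. Record draw and separation times. If chilling is meant for other analytes, say so separately for those tubes. In the section 7 schedule, state which draws include U&E.

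A single delivery at minute 90 would cut the supine wait from 210 to 60 min, but if U&E is taken at all four draws it would still wait 60 min longer than the last tube. Separating each tube within a fixed time of its own draw would remove that difference.

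The cost is a wording change and one delivery during the 4-hour visit, for which someone must be free to leave the study room. No extra blood is needed.
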